8.2 INFORMED CONSENT

The investigator will obtain written informed consent from the subject using the IRB/EC-approved consent form prior to initiation of any study-specific assessments or procedures. Consent is documented by the dated signatures of the subject the person conducting the consent discussion, and the investigator. Written informed consent must be obtained from a potential subject no more than 90 days prior to performing the study procedure.

Informed consent completion will be monitored regularly by the sponsor.

8.3 MOMENT OF ENROLLMENT

The subject will be considered "enrolled" in the study after the subject has met all inclusion and exclusion criteria, has signed the study informed consent form, and has completed the baseline assessments.

8.4 RANDOMIZATION AND SUBJECT IDENTIFICATION

Randomization will occur if the subject is deemed eligible following screening assessments and has signed the informed consent form. Subject identification number will be assigned at the time of randomization and the identification number will be retained throughout the study. No personal identifying information will be included on the case report forms.

8.5 SUBJECT DISCONTINUATION OR WITHDRAWAL

The investigator should instruct the subject regarding the importance of complying with the data collection and follow-up visit requirements. Poor subject adherence may result in the sponsor discontinuing the subject from the study.

Subjects may be involuntarily removed from the study for failure to adhere to the protocol, failure to attend follow-up visits, or due to safety reasons. In such cases, the investigator shall arrange for an exit visit and complete a study exit case report form for the subject.

Subjects may voluntarily withdraw from the study at any time without reason. The investigator shall make an effort to obtain an exit visit but cannot insist on the visit if the subject does not wish to come in. The investigator shall complete a study exit case report form with as much information as is available at the time of withdrawal.

A subject may be withdrawn after screening and before receiving the study treatment if, at the investigator's discretion, he or she has developed a general health condition that would increase risks from study treatment.

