16 STATISTICAL CONSIDERATIONS

16.1 GENERAL ANALYSIS PRINCIPLES

All primary endpoint analyses will be conducted under the principle of "Intention-To-Treat" (ITT), where each subject randomized to a treatment group who has met all inclusion/exclusion criteria and had a mapping and/or ablation catheter inserted shall be considered part of the ITT group. As a secondary exploratory analysis, a "Per Protocol" (PP) analysis may be performed with a subgroup of the ITT group who have no major protocol deviations reported.

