This endpoint will be evaluated using a Chi-Square test of independence, the proportions assumed to be binomial for each group.

C. Acute Safety (Primary safety endpoint)

The acute safety success of either treatment arm is defined as freedom from serious adverse events related to the procedure within ten (10) days of the index procedure. The proportion of successes in each arm will be calculated as follows:

$$\frac{n}{N}$$

Where:

n = the total count of subjects presenting freedom from serious adverse events related to the procedure within ten (10) days of the index procedure.

N = the total count of subjects in that arm in the ITT group

The statistical hypothesis for this endpoint is operationalized as follows:

$H_0: p_E = p_C$

$H_A: p_E \neq p_C$

Where:

p_E = the proportion of "successes" in the FIRM arm

p_C = the proportion of "successes" in the conventional ablation control arm

This endpoint will be evaluated using a Chi-Square test of independence, the proportions assumed to be binomial for each group.

D. Long-Term Safety (Primary safety endpoint)

Long-term safety is defined as freedom from procedure-related serious adverse events (SAEs) (including those related to repeat procedures) within one year of the initial procedure.

The statistical hypothesis for this endpoint is operationalized as follows:

$H_0: p_E = p_C$

$H_A: p_E \neq p_C$

$\alpha =$

Where:

p_E = the proportion of subjects free from serious adverse events related to the procedure (including from any repeat procedures required) within one year of the index procedure in the FIRM arm

p_C = the proportion of subjects free from serious adverse events related to the procedure (including from any repeat procedures required) within one year of the index procedure in the conventional ablation control arm

The proportion of events in each treatment arm shall be evaluated relative to their respective primary endpoint using both Chi-Square (Binomial, 1df) and by Kaplan-Meier survival estimation. Each evaluation will include 95% confidence intervals.

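### Section 8.5 lets treated subjects be removed from the study for non-adherence, missed visits or safety reasons, which ends collection of the one-year primary outcomes in subjects who remain in the ITT group

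*Protocol*

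**What the plan says.** Protocol Section 8.5 gives the sponsor and the investigator discretion to end participation. Of the sponsor it says: "Poor subject adherence may result in the sponsor discontinuing the subject from the study". More generally, subjects may be "involuntarily removed from the study for failure to adhere to the protocol, failure to attend follow-up visits, or due to safety reasons". What follows removal is limited: "In such cases, the investigator shall arrange for an exit visit and complete a study exit case report form for the subject". A separate last paragraph of 8.5 covers withdrawal after screening and before treatment, when a new health condition raises the risk.

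Section 16.1 states the analysis principle: "All primary endpoint analyses will be conducted under the principle of" intention to treat. Its ITT group consists of randomized subjects who "met all inclusion/exclusion criteria and had a mapping and/or ablation catheter inserted shall be considered part of the ITT group". Removal after the procedure does not take a subject out of that group.

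Two of the primary endpoints in Section 16.2 run to one year: single-procedure freedom from AF/AT recurrence over months 3 to 12 (16.2 A), and freedom from procedure-related SAEs, repeat procedures included (16.2 D). Both are to be analysed by chi-square and by Kaplan-Meier.

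**The concern.** The procedure on Day 0 is the whole study intervention. A treated subject has no remaining study treatment to stop, so removal from the study chiefly stops rhythm monitoring and SAE collection. The subject still counts in the ITT denominator but contributes no outcome after the exit visit. In the chi-square comparison that is a missing outcome. In Kaplan-Meier it would ordinarily be a censored time, and the estimate is valid only if censoring is unrelated to prognosis.

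There are plausible routes by which removal could relate to outcome. Section 10.3 sets a window in which anti-arrhythmic drugs must be stopped and makes out-of-window visits deviations. Section 13.4 lists medication non-compliance as a deviation. A subject whose symptoms keep him or her on a drug, or away from visits, could therefore be classed as non-adherent. Investigators perform the arm-specific procedure, so they know the allocation when they use this discretion. The statistical analysis plan can say how missing outcomes are handled, but it cannot recover data that were never collected.

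**Working it through.** **1. Does any other section restore follow-up after removal?**

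- Section 8.6 requires prompt contact and rescheduling after a missed visit, and three attempts before a subject is called lost. It does not cover a subject who has been removed, and it sits awkwardly with 8.5, which makes missed visits a ground for removal.
- Section 10.3 keeps subjects under follow-up after re-ablation. It covers re-ablation only.
- Section 11 follows adverse events until they resolve or are judged chronic or stable. For a removed subject this covers events already observed, not new ones.

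None of these continues rhythm or SAE collection to 12 months for a removed subject. A subject removed at Month 3 loses 12 − 3 = 9 months of safety observation and the whole 3-to-12-month effectiveness window.

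**2. How large could the effect be?** The protocol gives no removal rate, and its alpha and sample-size inputs are redacted, so there is no plan figure to reproduce. The only document input is up to 350 subjects randomized 1:1, or 350 / 2 = 175 per arm. All rates below are assumptions.

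Let p be the true success proportion in an arm, r the share removed with no failure yet documented, and s the success proportion that those removed subjects would have had. Then

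complete-case success = (p − r·s) / (1 − r).

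One arm, p = 0.60, r = 0.10:

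- all removed would fail (s = 0): 0.60 / 0.90 = 66.7%
- s = 0.30: (0.60 − 0.03) / 0.90 = 63.3%
- removal unrelated to outcome (s = 0.60): (0.60 − 0.06) / 0.90 = 60.0%, so no bias.

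**3. Between arms, with no true effect.** If removal is equal in both arms, the two complete-case proportions are equal: the difference is 0 and the false-positive rate stays at its nominal level. If 10% are removed in one arm and 5% in the other, and all would have failed, the difference is p/0.90 − p/0.95:

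| True success in both arms | 10% removed | 5% removed | Spurious difference | False-positive rate |
|---|---|---|---|---|
| 50% | 55.6% | 52.6% | 2.9 points | 8% |
| 60% | 66.7% | 63.2% | 3.5 points | 10% |
| 70% | 77.8% | 73.7% | 4.1 points | 14% |

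The last column uses a pooled two-proportion z-test on the subjects remaining (175 × 0.90 = 157.5 and 175 × 0.95 = 166.25) at an assumed two-sided alpha of 0.05. The arm with more removals looks better.

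**4. Sensitivity.**

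- 10% versus 5% with s = 0.30: 1.2 to 2.3 points, false-positive rate 5.5% to 7.6%.
- 15% versus 5% with s = 0: 6.2 to 8.7 points, 20% to 46%.
- 15% versus 5% with s = 0.30: 2.5 to 5.0 points, 7% to 17%.
- Any split with s = p: 0 points, 5%.

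**The case against.** The strongest reply is that the rule is permissive, that retention under 8.6 comes first, and that nothing shows removal would be frequent or differ by arm. Much outcome information is also safe. A recurrence documented before removal already counts as a failure. A subject removed because of a procedure-related SAE has already failed long-term safety. Re-ablated subjects are failures and are still followed. The exit visit captures status up to removal. Acute safety, read within ten days, is little affected, and the 3-month effectiveness endpoint is affected only by removals before that point. All of this stands. It limits the size of the problem but does not supply the missing follow-up.

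Three stronger readings are tempting, and the protocol does not support them.

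- A reader might infer that 8.5 breaches the ITT principle. It does not: Section 16.1 fixes membership by randomization, eligibility and catheter insertion, so removed subjects stay in the set. What suffers is outcome ascertainment within it.
- A reader might infer that the subjects removed are those most likely to fail. That is plausible, but the protocol neither states nor quantifies it.
- Because success means no documented episode, a reader might count every removed subject as a success. If 5% to 10% of one arm were removed and 40% of them recurred unseen, freedom in that arm would be overstated by 0.05 × 0.40 = 2 to 0.10 × 0.40 = 4 points. The protocol does not state that rule, and treatment of missing outcomes may properly sit in the statistical analysis plan. As a between-arm bias, the figure also needs no removals in the other arm.

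**Conclusion.** The point holds as a defect in what Section 8.5 permits. For treated subjects it ties non-adherence, missed visits and safety reasons to the end of data collection, although two primary endpoints need observation to one year and no other section restores it. Complete outcome ascertainment under ITT is undermined, with possibly informative censoring in Kaplan-Meier.

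The size cannot be determined from the protocol. The 3-to-4-point example rests on four assumptions: 10% versus 5% removal, true success of 50% to 70% in both arms, every removed subject being an undocumented failure, and a complete-case analysis. With equal removal there is no spurious difference under no true effect, although outcome-related removal still distorts each arm's own rate. The change is worth making because the lost data cannot be recovered later and preventing the loss is cheap.

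**What to change.** Amend Section 8.5 so that, for subjects in the ITT group (catheter inserted), non-adherence, missed visits and safety events do not end follow-up. Rhythm data, SAEs and vital status continue to be collected to 12 months, by telephone or from records where visits are missed. Follow-up ends early only if the subject withdraws consent, dies, or is lost to follow-up under Section 8.6.

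Leave the pre-treatment withdrawal paragraph of 8.5 unchanged, and do not extend the rule to subjects who never enter the ITT group, such as those in whom AF cannot be sustained (Section 10.2, Table 6). The change concerns data collection only and alters no clinical decision.

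The cost is protocol wording and some extra contact effort for poorly adherent subjects.

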8.6 CONTACT FOR FOLLOW-UP AND LOSS TO FOLLOW-UP

Subjects who miss a study visit should be contacted immediately by the Investigational Site to determine the reason for the missed visit and to reschedule the visit as soon as possible to meet the study visit window. If the subject cannot be located after 3 attempts through a variety of communication modes (phone, email, letter), then the subject will be considered lost to follow-up. The investigational sites should collect contact information (home phone, cell phone, fax, email, home address, etc.) from the subject in order to minimize loss to follow-up. All attempts to contact the subjects will be documented and retained in the subject study record.

9 INVESTIGATIVE SITES

Up to 25 investigational sites in Europe and North America will participate in this study.

9.1 INVESTIGATOR SELECTION

A. To qualify for participation, the study investigator will have completed the following:

- Undergone the standard training provided by Abbott EP/Topera, Inc. in the use of the RhythmView® system and analysis of FIRM maps produced by the system.
- Participated in 5 FIRM-guided procedures prior to enrolling any subjects in the study.

9.2 EQUIPMENT REQUIREMENT

A. In order to participate in this study, the site must also have the following equipment available:

- 64-pole mapping catheter (Topera FIRMap Catheter) and appropriate analyzer to acquire full chamber data (RA or LA) per Topera RhythmView system requirements.
- Topera RhythmView 3D electrophysiologic mapping system.
- Optionally, 3-D electroanatomic mapping system (CARTO, Biosense Webster, Velocity or Nav-X, St Jude Medical) compatible with FIRMap for documentation of lesions relative to recordings from mapping catheter.

9.3 INVESTIGATOR DISCONTINUATION

Prior to participation in the study, all investigators must sign the Protocol Signature Page which outlines the investigator's obligations in the study. The sponsor may elect to discontinue, or suspend, the investigator's participation in the study due to poor study compliance, lack of compliance with applicable regulations or IRB/EC requirements, or insufficient recruitment of study subjects.

10 STUDY FLOW AND VISIT SCHEDULE

The study will be conducted in three phases listed below and depicted in Figure 1.

1. Screening & Baseline
2. Study procedure through discharge
3. Follow-up periods

Each of these phases is discussed separately below, following Table 5 – Schedule of Assessments.

Figure 1 Study Flow

[figure not shown]

Table 5 - Schedule of Assessments

Event	Baseline	Procedure	Discharge	Day 7-10	1-month	3-month	6-month	12-month
Informed Consent	☒							
Demographics, Medical history, Cardiac diagnosis	☒							
Lab work per standard of care (including HCG for women of childbearing potential)	☒							
INR if patient is on Warfarin (as appropriate on post-procedure f/u)	☒	☒	☒	☒	☒	☒	☒	☒
TEE (when clinically indicated)	☒							
Diagnostic 12-lead ECG	☒	☒	☒	☒	☒	☒	☒	☒
Documentation of AF	☒							
Concomitant cardiac medications	☒	☒	☒	☒	☒	☒	☒	☒
NYHA Class Assessment	☒							
EQ-5D QoL Survey	☒			☒	☒	☒	☒	☒
AFEQT QoL Survey	☒			☒	☒	☒	☒	☒
AF Symptom and rhythm assessment	☒			☒	☒ (☒)	☒	☒	☒
AE review		☒		☒	☒ (☒)	☒	☒	☒
24 - 72 hr. ambulatory continuous ECG monitor, (Holter) or CIED					☒	☒	☒	☒
AF Interventional procedures performed (repeat ablation, AF-related hospitalization)					☒	☒	☒	☒

Legend:
 ☒ = Required ☐ = via Telephone ☒ = If applicable

10.1 SCREENING AND BASELINE

A. *Screening*

Patients at the investigational sites with persistent AF will be asked about their interest in study participation. For those patients who express an interest to participate, the inclusion/exclusion criteria will be reviewed against existing medical history and the results of any standard clinical work-up to assess preliminary eligibility. Potential patients who do not meet entrance criteria may, as appropriate, repeat screening evaluations at a later time for possible enrollment into the study.

B. *Baseline Assessment*

If the patient is not excluded on the basis of existing medical history and standard clinical work-up, the patient will be asked to provide informed consent to participate in the study. Baseline assessments include the following as shown in Table 5 – Schedule of Assessments.

- Determine study eligibility based on the requirements specified in the inclusion / exclusion criteria.
- Demographics.
- Medical history, including any hospitalizations or emergency room visits for episodes of all cardiac arrhythmias within six months of screening, all anti-arrhythmic drugs (AADs) and other cardiac medications.
- Reported incidence of at least two (2) documented episodes of persistent atrial fibrillation (AF) during the three months preceding trial entry (at least one episode should be documented by rhythm strip or ECG).
- Treatments administered for atrial fibrillation in the six months prior to enrollment, e.g., pharmacologic treatments and non-pharmacologic interventions. Medications should include dose and duration.
- Documentation of therapeutic International Normalization Ratio (INR) for three weeks prior to the procedure (if applicable per Inclusion Criteria) in cases of subjects taking warfarin.
- NYHA class.
- Current cardiac rhythm.
- Largest dimension left atrial diameter measured from transthoracic echo, cardiac CT or cardiac MR within the last 3 months with image documentation. Intracardiac echocardiographic measurement at the time of the procedure can alternatively be used to document this.
- Ejection fraction (EF) measured within the last 3 months or from the pre-procedure TEE or TTE.
- When clinically indicated, TEE will be performed within 72 hours prior to the ablation procedure. If any evidence of left atrial thrombus is discovered, then the ablation procedure will not be performed at that

time. The patient may be either excluded from the study or maintained on oral anticoagulation for an additional period of at least 6 weeks and re-tested (TEE repeated) for thrombi.

- 12-Lead ECG within 72 hours of study procedure.
- Cardiac medications currently prescribed for the subject's daily medical therapy.
- Pre-procedure laboratory values per standard practice.
- Neurological Exam (if clinically indicated) if symptoms suggestive of neurologic disease, and is to be performed by the neurology medical staff.
- Prior to the procedure, subjects fitting the investigator's standard criteria for anticoagulation will have been orally anti-coagulated (in case of Warfarin, with therapeutic INR (≥ 2.0) for at least three weeks prior to randomization, or they may be placed on therapeutic doses of subcutaneous low-molecular-weight heparin (LMWH)). As dictated by center clinical practice, oral anti-coagulation will be discontinued and either subcutaneous LMWH or IV heparin will be substituted at therapeutic doses until the time of the procedure. At the investigator's discretion, dabigatran, rivaroxaban or apixaban will be withheld for 24 hr. prior to the procedure.
- It is highly recommended that antiarrhythmic medications be stopped at least 3 days prior to the procedure; amiodarone should be stopped 30 days prior to procedure. Antiarrhythmic medications can resume following the procedure, at the investigator's discretion.
- EQ-5D and AFEQT Quality of Life surveys.
- Pregnancy test to be performed for women of child bearing potential.

Each site will maintain a screening log noting the reasons for screening failures.

10.2 STUDY PROCEDURE

The subject will be scheduled to undergo study treatment after the subject has met all inclusion and exclusion criteria, has signed the study informed consent form, and has completed the baseline assessments. Once enrolled in the study, the subject will be randomized to undergo either conventional AF treatment with ablation, or FIRM-guided procedure followed by conventional AF ablation.

A. *Pre-procedure Preparation*

Just prior to and/or during the procedure, a glycoprotein IIb/IIIa inhibitor or other platelet inhibitor may be administered if it is standard practice. The insertion of the FIRMap catheter or performing transseptal puncture, whichever comes first, will be followed immediately by an IV heparin bolus, followed by repeated heparin administration, adjusted as necessary to achieve and maintain an ACT above 300 seconds.

B. *Intra-procedure Guidelines*

During the procedure, the following actions should be taken and appropriate data collected. Table 6.

Table 6 – Intra-Procedure Guidelines

Parameter	Description
Vascular access	Under sterile technique, the right and/or left femoral veins may be cannulated via Seldinger, or percutaneous approach. Other vascular access also may be obtained based upon physician judgment.
Reference catheter placement	Reference catheters (including 64-pole FIRMap catheter(s)) may be inserted and placed within the heart to record signals as clinically required at the discretion of the physician.
Access to left atrium	Access to the left atrium should be according to the institution's standard practice.
Anticoagulation	Upon insertion of 64-pole FIRMap catheter or transseptal puncture (whichever comes first), an IV heparin bolus should be administered, followed by repeated heparin administration, adjusted as necessary to achieve and maintain an ACT above 300 sec.
Catheter placement	Catheters may be inserted and used according to the institution's standard practice.
Source arrhythmia diagnosis	After obtaining at least 1 minute of continuous electrograms from the 64-pole FIRMap catheter either simultaneously or sequentially in the right and left atria, these electrogram data will be transferred to the Topera RhythmView® system. This will then produce FIRMap displays which will be interpreted by the operator to determine which locations have focal or rotor rhythms that could be sources of the AF.
3-D Electroanatomic Mapping	3-D electroanatomic maps may be created using CARTO (Biosense Webster, Johnson & Johnson) or Nav-X (St. Jude Medical) systems for documentation of anatomy and ablation lesion locations.
Induction of sustained AF	If the patient is not experiencing spontaneous, sustained AF (>5 min uninterrupted), induce sustained AF by atrial burst pacing, typically from the coronary sinus, with or without isoproterenol infusion in conventional clinical fashion. IF AF CANNOT BE SUSTAINED, THE PATIENT DOES NOT MEET THE INCLUSION CRITERIA FOR THE PROTOCOL AND THE PATIENT WILL UNDERGO CONVENTIONAL AF ABLATION PER PHYSICIAN DISCRETION.

Ablation data	For each ablation, the following data will be recorded: time, catheter size, lesion number, phrenic nerve assessment (if in an area of potential phrenic nerve proximity), approximate catheter tip location, duration of application, average temperature, and any comments.
FIRM-guided procedure	Under fluoroscopic guidance, a cardiac ablation catheter is passed to the location(s) identified as AF source rhythms (rotors or focal impulses). Therapy can be applied at up to 6 sites identified by the initial or repeated FIRMap per standard practice.
Conventional Ablation	Conventional ablation typically consists of isolation of all four pulmonary veins per guidelines. In addition, in the conventional arm of the study, data will be recorded regarding any additional ablation such as that performed per local routine for AF (e.g. CFAE, roof line, additional trigger elimination, etc.). Such additional ablation is NOT typically performed in the FIRM-guided limb where only PVI is typically performed for the purposes of AF ablation beyond FIRM-guided locations.
Additional ablation for other arrhythmias (non-AF)	Additional ablation for other arrhythmias will be noted for atrial tachycardia (AT) and/or right cavo-tricuspid isthmus ablation in the event that the patient has documented AT/atrial flutter prior to or during the procedure.
Electrograms	Electrogram recordings evaluating conduction into or out of each treated vein.
ACT values	Activated Clotting Times (ACT) value is first measured prior to insertion of FIRMap catheter or trans-septal puncture, whichever comes first, to determine baseline value and then every ten minutes post-heparinization until therapeutic and, subsequently, every 30 minutes during left-atrial access. (Heparin dosage should be adjusted to maintain ACT above 300 sec). The ACT will be monitored every 10 minutes following initial heparin delivery until the target value is achieved and subsequently checked at least every thirty minutes during the procedure.
Vascular access sheath removal	The vascular access sheaths will be removed when the ACT reaches a clinically acceptable level.

The following precautions should be taken per standard of practice:

- Typically, in order to reduce the risk of introducing air emboli through a transseptal sheath into the left atrium, the following precautions are taken:
 - Aspiration or spontaneous bleed back from the trans-septal sheath side-port may be performed after each catheter withdrawal;

- Trans-septal catheter insertion and withdrawal will always be performed slowly;
- Unnecessary catheter exchanges may be avoided;
- The time any trans-septal sheath is through the septum may be minimized; and
- The time multiple sheaths cross the septum may be minimized.
- Just prior to ablation, at each ablation site in the posterior LA or RA, pacing at high output (>15 mA) from the ablation catheter tip or fluoroscopic visualization of diaphragmatic movement may be used to assess whether the phrenic nerve is in proximity to the ablation zone. These data will be documented and used to guide ablation at each site.
- Esophageal temperature monitoring during ablation in the posterior LA, per local standard of care, may also be considered.

C. *Intra-procedure Measurements*

The following data will be collected during the procedure.

Table 7.

Data	Description
Fluoroscopy times	
To be recorded:
 
Total fluoroscopy time
 
 ● The total fluoroscopy time for the procedure (a.k.a., “pedal down” time) 
Ablation time
 
 ● The time between the first ablation catheter insertion to last ablation catheter removal from the left atrium.
Total RF ablation time	
Total RF ablation time as measured by total time of ablation lesion applications, from first ablation lesion to end of last lesion, will be documented. These values will be noted in both the FIRM-guided and conventional ablation groups. If ablation for AT/atrial flutter is pursued, this ablation time will be documented separately

Total procedure time	
Total procedure time defined as: time from insertion of first sheaths for vascular access to removal of sheaths.

Medication administration	
Cardiac medications administered during the procedure including drug name, dosage, and indication and will be recorded.

Devices and equipment	
Devices and equipment used during the procedure including access devices, diagnostic and ablation catheters, and mapping equipment type will be recorded.

D. Post-procedure & Discharge Requirements

The measurements and evaluations that will occur at post-procedure are provided below.

- Post-ablation and following recovery from anesthesia, subjects will be monitored until stable.
- Once the sheaths have been removed and hemostasis has been achieved, heparin or LMWH will be restarted along with oral anticoagulation (warfarin or novel oral anticoagulants (e.g. dabigatran, rivaroxaban, apixaban)).

The platelet inhibitor (if administered during the procedure) and heparin or LMWH will be continued until the INR exceeds 2.0 (in the case of warfarin use for longer term oral anticoagulation).

Oral anti-coagulation will continue for at least three months after the procedure. Subjects who were on oral anticoagulation pre-procedure will be maintained on anticoagulation for the duration of the study.

Note: Oral Glycoprotein IIb/IIIa Inhibitors use is discouraged during the follow-up period.

- Post-procedure drug therapy will include re-initiation and/or continuation of any pre-procedure cardiac medications including all anti-arrhythmic drugs used for the treatment of atrial flutter or other arrhythmias/cardiac diseases. Supplemental anti-arrhythmic medications will be administered under the direction of the investigator and documented in the appropriate section(s) of the case report forms.
- Post procedure rhythm monitoring will occur either via a Cardiac Implanted Electronic Device (CIED) with interrogation at intervals per protocol or all subjects without CIED will receive a 24 – 72 hour Holter monitor at 1, 3, 6, and 12 months post-procedure. If AF symptoms are documented as recurrent AF within the follow-up period, further treatment shall be at the discretion of the physician (e.g., drugs, re-ablation, etc.).
- Pre-discharge evaluation will include:
 - Diagnostic 12-lead ECG
 - Symptom and rhythm assessment
 - Antiarrhythmic medications
 - Adverse events

